10. STUDY OUTCOMES

- a) **Primary Outcome Measure(s)** - describe how you will measure the primary and other outcomes of the study (e.g., blood pressure change, changes in visual acuity using a specific test, pain scales, responses on a questionnaire, etc.). Upload copies of your data collection tools and/or a list of all variables/data points you will collect.

Note: Primary outcome measures may be measured in various ways such as:

- binary (e.g. improvement in symptoms vs. no improvement in symptoms)
- continuous (e.g. weight - kg, blood loss - mL)
- ordinal (e.g. pain - mild, moderate, severe)
- time to event (e.g. survival)
- counts (e.g. number of infections, number of events occurring)

Response:

Primary outcome measures include:

- 1) **Desaturation to less than 95% for more than 10 seconds;**
- 2) **Episodes of persistent cough, defined as 3 or more consecutive coughs;**
- 3) **Episodes of complete or partial laryngospasm;**
- 4) **Episodes of bronchospasm;**
- 5) **Incidence of negative pressure pulmonary edema;**
- 6) **Obstruction that requires maneuvers, oral airway or jaw thrust**

- b) Describe any secondary or other outcomes (exploratory):

Secondary outcome measures include:

- 1) **Length of time from end of surgery to leaving the operating room;**
- 2) **Length of stay from admission to and discharge from the PACU Stage 1 and 2;**
- 3) **Incidence of unexpected hospital stay related to perioperative respiratory complications.**
- 4) **Incidence of sore throat**

11. HYPOTHESES

Hypotheses are more specific than specific aims and are tested using predetermined statistical methods and form the basis for statistical power calculations. The primary hypothesis is a statement of the effect of the research intervention/interaction on the primary outcome measure. Hypotheses are generally stated as the null and alternative hypotheses (H_0 , H_a) as they have their basis in inferential statistics. Rejecting the null hypothesis with a specific level of probability indicates that there is a relationship between the variables being studied. State the alternative hypothesis which you expect your data to support.

Examples of null and alternative hypotheses

- H_0 : Chronic sinusitis prevalence rates are not different among children from low and high socioeconomic groups
- H_a : Chronic sinusitis prevalence rates are different among children from low and high socioeconomic groups.

a) Describe the primary hypothesis:

Response:

H_0 : The rate of perioperative respiratory complications of deep extubation in adults undergoing head and neck surgery at MEE is not different among other institutions.

H_a : The rate of perioperative respiratory complications of deep extubation in adults undergoing head and neck surgery at MEE is different than other institutions.

b) Describe any secondary hypotheses.

Response:

- 1) Length of time from end of surgery to leaving the operating room;
- 2) Length of stay from admission to and discharge from the PACU Stage 1 and 2;
- 3) Incidence of unexpected hospital stay related to perioperative respiratory complications.
- 4) Incidence of sore throat.

Is there a significant association between the lengths of time from end of surgery to leaving the operating room with the perioperative respiratory complications?

Is there a significant relationship between the lengths of stay from admission to and discharge from the PACU?

What is the incidence of unexpected hospital stay associated with perioperative respiratory complications?

What is the incidence of sore throat?

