2. SPECIFIC AIMS

List the specific aim(s) and objective (s) of the study (i.e., what does the study hope to accomplish). Include any secondary and exploratory aims and objectives (e.g., biomarkers, genetic analyses).

Response: To assess the perioperative respiratory complications rate of deep extubation in adult patients undergoing head and neck surgery at MEE.

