3. BACKGROUND AND SIGNIFICANCE

Describe the scientific background and rationale for the study.

- Provide a critical review of the relevant literature and the state of current knowledge on the topic. Discuss deficiencies or gaps in knowledge that make the study worth doing. Include a list of literature cited in an appendix at the end of this protocol.
- Discuss the importance of the topic with respect to scientific knowledge, clinical practice, public health, impact on individuals/community, incidence, prevalence, mortality and morbidity, as applicable.

Response:

Tracheal extubation in patients undergoing head and neck surgery may be followed by several respiratory complications, such as coughing, desaturation, laryngospasm, bronchospasm, and airway obstructions.^{1,2} The trachea can be extubated when the patient is still deeply anaesthetized or after he/she fully regains consciousness. Currently, the default method of extubation at Massachusetts Eye and Ear Infirmary (MEEI) is deep extubation. In contrast, the default method of extubation in most centers in the United States is awake extubation.

Respiratory complications may occur following both deep and awake extubation, and the superiority of one method over another has not been established. When the trachea is extubated in light stages of anesthesia or after the patient has regained consciousness, there can be significant increases in heart rate and arterial pressure that may continue into the recovery period. This increase in blood pressure and heart rate may be partially due to straining during extubation. In patients in whom these stimulatory effects can be detrimental, tracheal extubation under deep anesthesia may reduce the incidence and degree of these complications; however, tracheal extubation under deep anesthesia may cause respiratory complications, including laryngospasm, bronchospasm, and negative pressure pulmonary edema.³

There is a paucity of research related to deep or awake extubation in adults. Specifically, such studies are lacking in patients who undergo head and neck surgery. In a prospective survey of respiratory complications of tracheal intubation and extubation of 1005 patients 16 years or older who underwent elective general anesthesia, Asai et al found that the incidence of respiratory complications was higher in the deep versus the awake extubation group, regardless of the type of operation.³

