5. SUBJECT INFORMATION

- a) Target Enrollment- Specify the number of subjects you plan to enroll and justify why this number is sufficient to achieve adequate power for statistical analysis taking into account anticipated screen failures and drop-outs. Include sample size by cohort if the study has multiple cohorts.

Response: Our proposed sample size of 300 patients will enable us to report the complication rates with adequate precision in terms of a sufficiently narrow two-sided 95% confidence interval. For example, if the observed respiratory complication rate is 30%, as was reported by Asai T et al (1), our confidence interval will have a half-width of 5%. If a complication rate that we observe is 35%, the half-width of our confidence interval will be 6% (nQuery Advisor version 7). We have used nQuery Advisor version 7 for the calculation of our sample size. For a CI of 95%, $\alpha = 0.05$, $P = 80\%$, and a complication rate of deep extubation of 30%, as reported by Asai T et al (Asai T, Koga K, Vaughan RS, et al. Respiratory complications associated with tracheal intubation and extubation. *Br. J. Anesth.* 1998, 80, 767–775.), we will require a sample size of 300.

- b) If this is a multi-center study and other sites rely on the MEE HSC as the IRB of record, please specify the total number of subjects required by all sites to achieve sufficient power.

Response: N/A

- c) Provide justification that the researchers have access to sufficient numbers of eligible subjects to meet target enrollment goals (e.g., researcher’s own patients, clinic patients with a specific diagnosis, subjects from previous studies who agree to participate in future studies).

Response: Potentially eligible subjects for this study are all adult patients who undergo head and neck surgery as well as deep extubation at the end of the surgery per the discretion of the anesthesiologist assigned to the case. Deep extubation is the default extubation method practiced at MEE. Therefore, there will be a sufficient number of potentially eligible subjects to meet the target enrollment goals.

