6. ELIGIBILITY CRITERIA

- a) Inclusion Criteria - Inclusion criteria are the specific characteristics of the study population(s) required for study enrollment (e.g., ages, gender, condition or disease.) List the inclusion criteria in a bulleted list.

Response: Adult men and women who present to MEE for head and neck surgery and undergo deep extubation will be included.

- b) Exclusion Criteria - Provide specific criteria for determining ineligibility to participate. Provide justification for their exclusion (e.g., pregnant women).

Note: Exclusion criteria are not always clinical in nature. Exclusion may also include circumstances that interfere with:

- the participant’s ability to give informed consent (diminished cognitive capacity or a language other than English and an interpreter unavailable)
- contraindications to the study treatment(s)/procedure(s)
- taking certain concomitant medication(s) or
- conditions that interfere with a patient's ability to comply with all study procedure(s)

Response: We do not exclude anyone from the study.

NOTE: Per federal regulations, the risks and benefits of research must be fairly distributed among the populations that could benefit from the research. No groups of persons (e.g., gender, pregnant women, children, minorities, non-English speakers) should be categorically excluded from research without a valid scientific or ethical reason to exclude such groups.

- c) Describe your rationale that the study population is representative of populations that may potentially benefit from the research, or the rationale for excluding certain groups, if applicable.

Response: N/A

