12. STATISTICAL METHODS

Describe the planned statistical methods including specific tests (e.g., parametric and non-parametric tests, estimation of incidence and prevalence rates, odds ratios, survival/failure analyses, intent to treat analyses). Provide the power calculations used to estimate the proposed sample size. If needed, please consult a biostatistician. (Note: Biostatistical consults are available through Harvard Catalyst.)

Response:

Our proposed sample size of 300 patients will enable us to report the complication rates with adequate precision in terms of a sufficiently narrow two-sided 95% confidence interval. For example, if the observed respiratory complication rate is 30%, as was reported by Asai T et al (1), our confidence interval will have a half-width of 5%. If a complication rate that we observe is 35%, the half-width of our confidence interval will be 6% (nQuery Advisor version 7). We have used nQuery Advisor version 7 for the calculation of our sample size. For a CI of 95%, $\alpha = 0.05$, $P = 80\%$, and a complication rate of deep extubation of 30%, as reported by Asai T et al (Asai T, Koga K, Vaughan RS, et al. Respiratory complications associated with tracheal intubation and extubation. Br. J. Anesth. 1998, 80, 767–775.), we will require a sample size of 300.

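### The primary hypothesis (Section 11a) compares MEE with other institutions, but the plan is a single-site estimate with no comparator, null value or test

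*Combined protocol and SAP*

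**What the plan says.** Section 11a states a null and an alternative hypothesis about how the MEE complication rate compares with that of other institutions. The alternative reads: "The rate of perioperative respiratory complications of deep extubation in adults undergoing head and neck surgery at MEE is different than other institutions". No institution, dataset or numerical rate is named.

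The other sections describe something narrower:

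- Section 2 gives the aim: "To assess the perioperative respiratory complications rate of deep extubation in adult patients undergoing head and neck surgery at MEE".
- Section 6a defines one group: "Adult men and women who present to MEE for head and neck surgery and undergo deep extubation will be included". Section 5b, on other sites, is answered N/A, and Section 18d, on samples or data from outside, is answered No.
- Section 12 says that 300 patients "will enable us to report the complication rates with adequate precision in terms of a sufficiently narrow two-sided 95% confidence interval". It gives half-widths of 5% at an observed rate of 30% and 6% at 35%.
- Sections 5a and 12 then list a 95% confidence level, alpha of 0.05, P of 80% "and a complication rate of deep extubation of 30" per cent, taken from a published survey.
- Section 3 describes that survey as covering "1005 patients 16 years or older who underwent elective general anesthesia". Of research on deep or awake extubation in adults it says: "Specifically, such studies are lacking in patients who undergo head and neck surgery".

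**The concern.** A primary hypothesis of difference needs something to differ from. This plan collects data at one site and never says which outside rate is the reference, how firmly that rate is known, which test applies, or what result would count as a difference. The form's own instructions in Section 11 say that hypotheses are to be tested by methods fixed in advance and are to underlie the power calculation. Neither condition is met.

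If the plan is followed as written, there are two likely outcomes. Either the primary hypothesis is never addressed, or someone checks afterwards whether the MEE confidence interval covers 30% and reports the answer as a between-institution finding. Such a finding could not be separated from differences in case mix, differences in outcome definitions, or sampling error in the published rate.

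**Working it through.** **1. The plan's own figures.** Inputs from Section 12: n = 300, two-sided 95% interval, observed rates of 30% and 35%.

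- Simple normal interval, 1.96 × √(p(1−p)/300): 5.19 points at 30% and 5.40 points at 35%.
- Exact (Clopper-Pearson) interval: 90/300 gives 24.87% to 35.53%, half-width 5.33 points; 105/300 gives 29.61% to 40.69%, half-width 5.54 points.

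The exact half-widths round to the stated 5% and 6%. The sample size therefore holds as a precision argument.

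**2. The power statement.** Power for a test of a rate needs a null rate and an alternative rate. Sections 5a and 12 give one rate, 30%. P of 80% cannot be reproduced, whatever P is meant to be (presumably power).

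**3. What n = 300 could detect if 30% were the null.** This is an illustration: the plan does not designate 30% as a null. Assume a fixed null of 0.30, a two-sided 5% test and a single look.

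Power = Φ[(|p₁ − 0.30|√300 − 1.96√(0.30 × 0.70)) / √(p₁(1 − p₁))]

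- At p₁ = 0.35: (0.8660 − 0.8982)/0.4770 = −0.067, so power is about 47%. At p₁ = 0.25 it is also about 47%.
- 80% power is reached at p₁ of about 0.375 or above, or about 0.228 or below.
- Exact binomial check: reject at 74 or fewer events or 107 or more, actual size 0.044; 80% power at about 0.379 or 0.228.

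**4. Treating a published rate as fixed.** Suppose the published 30% came from m deep extubations and the true rates are equal. The actual two-sided error of a nominal 5% test is then

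2 × [1 − Φ(1.96 × √((1/300)/(1/300 + 1/m)))]

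| m (assumed) | Actual error |
|---|---|
| 100 | 33% |
| 300 | 17% |
| 500 | 12% |
| 1005 | 8.5% |

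The documents do not give m. They give only the survey total of 1005, so the last row is a lower bound on the error, reached only if every surveyed patient had been extubated deep.

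**5. The interim analysis.** Section 20a plans one at half enrolment (150 patients) and does not say what is tested. If both looks tested against 30% at a nominal 5% (assumed), the overall two-sided error would be about 8.3% by normal approximation, or 7.0% by exact binomial with limits of 33/57 events at 150 patients and 74/107 at 300.

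**The case against.** The strongest reply is that 30%, alpha of 0.05 and P of 80% appear in one sentence, so 30% is an implied benchmark, and a 95% interval doubles as a 5% test against any fixed value. That shows a reference figure is present in the document. It does not show that one was chosen: the text uses 30% as an example of an observed rate and as a planning rate, never as a null, and gives no alternative. Nor does the figure match the hypothesis. By Section 3's description it comes from a single survey of elective general anesthesia, not from head and neck surgery elsewhere.

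A second reply is that the form invites a null and an alternative, and that aim, design and methods otherwise agree on estimation. This stands in part. It limits the consequence, because the planned intervals are unaffected, but the hypothesis pair is still the investigators' own stated primary hypothesis.

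Three cautions are fair:

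- Section 18d sits in a privacy section concerned largely with samples and transfer agreements, so its No does not by itself exclude use of a published aggregate rate. The single-site reading rests mainly on Sections 2, 5b and 6a.
- Section 13 says awake extubation is the default almost everywhere else. That patients extubated deep elsewhere may be more selected than at MEE is an inference from this, and the point does not need it.
- Steps 3 to 5 of the working rest on assumed inputs and only illustrate what a comparison would face.

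**Conclusion.** The concern holds. Section 11a claims a comparison that the design and analysis cannot deliver, and the 80% figure has no null, alternative or test behind it. This conclusion follows from the text alone and needs no assumption.

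The damage is confined to the hypothesis and the power statement. The sample size of 300 and the stated half-widths stand. If a comparison with 30% were attempted, the study would be adequately powered only for differences of roughly 7 to 8 points, taking 30% as fixed and a single look. Uncertainty in the published rate would raise the false-positive rate above 5% by an amount the documents do not allow one to pin down. This should be fixed before the results are analysed.

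**What to change.** Replace the hypothesis pair in Section 11a with an estimation objective that matches Section 2, for example: *Rates of perioperative respiratory complications after deep extubation at MEE will be estimated with two-sided 95% confidence intervals; no formal test against other institutions will be made.* Since Section 10a lists six primary outcomes and no composite, the same sentence should say whether it means six rates or one any-complication rate. That is a separate matter, but it is easily settled here.

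In Sections 5a and 12, keep the half-width justification. Remove P of 80%, or define it and attach the alternative rate and the test. Cite the published 30% as context only, with its population stated.

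If the sponsor prefers to keep a comparison, the plan must specify in advance the reference rate and the number of patients behind it, a matching endpoint, the test, the power at 300 patients, and how the half-enrolment analysis in Section 20a is handled.

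The first route costs text edits to Sections 5a, 11a and 12, with no extra patients or data; the sponsor gives up a between-institution claim that the design cannot support. The second also requires a documented reference rate with its sample size and a rule controlling error at the interim look.

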12. STATISTICAL METHODS

Describe the planned statistical methods including specific tests (e.g., parametric and non-parametric tests, estimation of incidence and prevalence rates, odds ratios, survival/failure analyses, intent to treat analyses). Provide the power calculations used to estimate the proposed sample size. If needed, please consult a biostatistician. (Note: Biostatistical consults are available through Harvard Catalyst.)

Response:

Our proposed sample size of 300 patients will enable us to report the complication rates with adequate precision in terms of a sufficiently narrow two-sided 95% confidence interval. For example, if the observed respiratory complication rate is 30%, as was reported by Asai T et al (1), our confidence interval will have a half-width of 5%. If a complication rate that we observe is 35%, the half-width of our confidence interval will be 6% (nQuery Advisor version 7). We have used nQuery Advisor version 7 for the calculation of our sample size. For a CI of 95%, $\alpha = 0.05$, $P = 80\%$, and a complication rate of deep extubation of 30%, as reported by Asai T et al (Asai T, Koga K, Vaughan RS, et al. Respiratory complications associated with tracheal intubation and extubation. Br. J. Anesth. 1998, 80, 767–775.), we will require a sample size of 300.

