15. BENEFITS

- a) Will individual subjects have any direct benefits from the research? If subjects will not experience direct benefit, state so.

Response: Subjects will not receive any direct benefits.

- b) Explain the potential benefits to science, and/or society as a result of this research.

Response: As deep extubation is the default method at MEEI, our study might be able to illustrate and elucidate the safety features as well as the rate of different respiratory complications of the deep extubation in adult patients undergoing head and neck surgery.

- c) If this study is more than minimal risk, explain how the risks are minimized in relation to the anticipated benefits of the study:

Response: N/A

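### Do Sections 5a and 12 have to name a confidence-interval method before the complication rates can be reported?

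*Combined protocol and SAP*

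**What the plan says.** Sections 5a (Target Enrollment) and 12 (Statistical Methods) carry the same paragraph. It commits the study to "report the complication rates with adequate precision in terms of a sufficiently narrow two-sided 95% confidence interval". It gives two worked cases for 300 patients. At an observed rate of 30%, "our confidence interval will have a half-width of 5" percent; at 35%, "the half-width of our confidence interval will be 6" percent. nQuery Advisor version 7 is cited as the software. A closing sentence lists a 95% confidence level, alpha of 0.05, P = 80% and a 30% rate as leading to 300 patients. P is not defined, and no alternative rate, margin or target width goes with it.

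No section names an interval method such as Wald, Wilson or exact.

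Section 10(a) lists six primary outcomes, one of which is "Incidence of negative pressure pulmonary edema". No expected rate is given for any of them. Section 15(b) says the study might throw light on safety features and on "the rate of different respiratory complications of the deep extubation", so rates for individual complications are evidently meant to be reported.

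**The concern.** The confidence interval is the only inferential output that the methods section promises, so its method would normally be stated. For a rate near 30% in 300 patients this hardly matters. With very few events it can. A Wald interval collapses to zero width when nobody has the event, and its lower limit falls below zero at 1 to 3 events. A report giving 0% to 0% for a respiratory complication would suggest that it cannot happen, although 0 of 300 is compatible with a true rate of about 1 in 82. In a study describing the safety of deep extubation, that error is in the reassuring direction. The undefined P = 80% adds to the impression that the statistical paragraph was not thought through.

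**Working it through.** **Inputs.** From Sections 5a and 12: n = 300, two-sided 95% level (z = 1.96), rates of 30% (90/300) and 35% (105/300), stated half-widths of 5% and 6%. The documents give no rate for a single outcome, so the low event counts and low true rates below are assumptions, shown over a range. All intervals treat each patient as having or not having the event.

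**Step 1: reproduce the plan's half-widths.**

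- Wald, z·√(p(1−p)/n): 1.96 × √(0.30 × 0.70/300) = 5.19 points; 1.96 × √(0.35 × 0.65/300) = 5.40 points.
- Wald with continuity correction, adding 1/(2n) = 1/600 = 0.17 points: 5.35 and 5.56.
- Exact (Clopper-Pearson): limits 24.87% to 35.53% and 29.61% to 40.69%, so half-widths of 5.33 and 5.54.
- Wilson: 5.16 and 5.37.

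Rounded to whole percents, the exact and continuity-corrected intervals give 5 and 6, as the plan states. Wald and Wilson give 5 and 5. The plan's figures are therefore correct under a standard method. Across the four methods the half-width runs from 5.16 to 5.35 at 30% and from 5.37 to 5.56 at 35%, a spread of about 0.2 points.

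**Step 2: few events, n = 300.** With 0 events the exact upper limit is 1 − 0.025^(1/300) = 1.22%, and the Wilson upper limit is z²/(n + z²) = 3.84/303.84 = 1.26%.

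| Events | Wald | Exact | Wilson |
|---|---|---|---|
| 0 | 0% to 0% | 0% to 1.22% | 0% to 1.26% |
| 1 | −0.32% to 0.99% | 0.01% to 1.84% | 0.06% to 1.86% |
| 3 | −0.13% to 2.13% | 0.21% to 2.89% | 0.34% to 2.90% |
| 5 | 0.22% to 3.12% | 0.54% to 3.85% | 0.71% to 3.84% |

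Exact and Wilson agree closely; Wald is the outlier. The continuity-corrected Wald interval, which also fits the plan's 5% and 6%, gives −0.17% to 0.17% at 0 events and −0.49% to 1.15% at 1 event, so it is poor there too.

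**Step 3: coverage of a nominal 95% interval, by true rate.** Wald against exact: 26% v 99.6% at 0.1%; 78% v 98% at 0.5%; 80% v 99% at 1%; 93% v 96% at 2%; 95% v 96% at 30%. The probability of no events, (1 − p)^300, is 74%, 22%, 5% and 0.2% at true rates of 0.1%, 0.5%, 1% and 2%. The Wald problem is thus largely confined to true rates of about 1% or less.

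**Step 4: P = 80%.** No formula in Step 1 contains a power term. Read as power for a two-sided one-sample test against 30% with 300 patients, 80% would correspond to a true rate of about 37.5% or 22.8%; the plan states neither. The phrase is surplus: it contradicts no stated figure and alters no interval.

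**The case for a change.** The best case for a change is that the text permits plain Wald, and that an outcome such as negative pressure pulmonary edema could well produce no events in 300 patients. Planning figures do not bind the analysis. The 5% and 6% also fit a continuity-corrected interval, so they do not single out the exact method. Software that truncates at zero would hide the negative limits. Naming a method would cost one sentence.

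Most of this stands as description. No method is written down, the two half-widths narrow the choice without fixing it, and Wald is unsuitable with few events. What does not stand is the step from there to a defect in the plan. The documents do not say that any outcome is rare, and they do not propose Wald. An interval of 0% to 0%, or a negative limit, is a plain signal to use another method. Truncation can mask the negative limit at 1 to 3 events, but at 0 events the zero-width interval remains in view. Section 15(b) is too hedged to carry more weight: it supports reporting individual rates and makes no claim about how precisely a rare one will be bounded.

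**Conclusion.** No change to the plan is needed. The missing method name is a detail that an analyst fills when reporting. The plan's own half-widths reproduce with an exact interval, and at 30% and 35% the choice among common methods moves the half-width by about 0.2 points. The sample size of 300 is unaffected.

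The largest effect is an upper limit of 0% instead of about 1.2% for an outcome with no events, and one about 0.8 to 0.9 points too low with 1 to 3 events. It arises only if such an outcome occurs and plain Wald is used despite its evident failure. Both conditions are assumptions; neither follows from the documents. The conclusion also takes each rate as the proportion of patients with at least one event. P = 80% is an undefined leftover with no bearing on any interval.
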